The concept of the glycemic index has been expanded over the years, giving rise to mathematical products such as the glycemic load (GL), which is defined as the quantity and quality of carbohydrates consumed and estimates the total glycemic effect of the diet, for its obtaining it is necessary to multiply the amount of CHO contained in the food ingested by the GI value ($GL = GI \times \text{available carbohydrates}$).

The increase to the glycemic load is associated with an unfavorable physiological response, mainly for people living with diabetes, since blood glucose and insulin values rise sharply. Foods with $GL \leq 10$ are considered low GL and foods with $GL \geq 20$ are considered high GL.

OBJECTIVES

General objective

To evaluate the *in vivo* bioavailability of bioactive compounds from a *H. sabdariffa* beverage and their immunomodulatory potential against moderate inflammation caused by SARS-CoV2 as well as enzymatic inhibition of α -amylase and α -glucosidase enzymes *in vitro*.

Specific objectives

1. To perform HPLC-DAD-MS characterization of a *Hibiscus sabdariffa* hibiscus-based beverage.
2. To perform an acute single-blind clinical trial, administering a hibiscus drink to normal-weight adults.
3. To evaluate the bioavailability of organic acids and phenolic compounds in urine and plasma samples present in the *H. sabdariffa* beverage.
4. To evaluate the immunomodulatory potential of the metabolites identified as bioavailable in plasma samples.
5. To evaluate the enzymatic inhibition of α -amylase and α -glucosidase exerted by the digested, placebo and treatment beverages.
6. To evaluate the *in vivo* GR and IR of the placebo beverage and treatment beverage.

. GENERAL METHODOLOGY

First Stage

Obtaining hibiscus-based beverage and placebo.

The hibiscus-based beverages (H.sabdariffa) and placebo were obtained from the reformulated company NUTRIYÉ SAPI de CV, located in the city of Guadalajara, Jalisco, Mexico.

Participants.

Twelve normo-weight volunteer participants without any medical condition were included. The invitation to participate was made through ITESO's communications office, as well as through announcements in social networks. They were selected according to the following criteria:

Within the inclusion criteria to be considered are those mentioned in Table 4.2.

Table 4.2. Non-inclusion and inclusion criteria for volunteer selection.

Inclusion criteria		Non-inclusion criteria	
Normolipidemia	Total cholesterol (plasma) < 200 mg/L-1	Hypertension	Hyperthyroidism
	Triglycerides < 150 mg/L-1	Diabetes	In diet
	Fasting glucose (plasma) < 100 mg/L-1	Smokers	Pregnant or lactating women
Normoglycemia	18.5 – 24.9	Cardiovascular disease	In medical treatment / supplements
BMI [kg/m2]	18 – 40	Secondary	Hepatic insufficiency

Abdominal circumference [cm].	Men < 90 Women < 80	hyperlipidemia Renal insufficiency	Infection / inflammatory disease (6 weeks prior to study)
Fat percentage [%] [cm]	Men < 19 Women < 33		
Systolic pressure [mmHg].	< 140		
Diastolic pressure [mmHg].	< 90		
Alcohol	Last consumption one week and a half		

The study adhered to the ethical principles for research on human subjects of the Declaration of Helsinki and was submitted to the ITESO Research Ethics Committee.

Acute Trial Clinical Intervention

An acute single-blind trial was conducted. Participants consumed a hibiscus-based drink (*H. sabdariffa*), or a 60ml placebo drink, and then received a Western-type diet characterized by excessive consumption of red meat, simple carbohydrates, ultra-processed products, colorants, saturated fats, refined sugars and very little intake of fiber and vitamins. After a washout period of more than 6 days, the participants underwent a second intervention with a different product from the first one (beverage to be evaluated or placebo, as appropriate), and the samples were repeated according to the following scheme

The protocol was previously explained to the volunteers and all those who give their written informed consent will be candidates to participate (Annex 1). On the day of the intervention, participants will arrive at 7 a.m., Mexico Central Time, with an overnight fast of 10-12h. They were requested a rest period of 30 min prior to blood pressure taking at the time of admission, in addition to the fact that they had to be seated, upright and with their feet on the floor during the process; the measurement was performed using a manometer on the left arm, elevated at the level of the heart (Gómez-León Mandujano et al., 2016).

Two types of sampling were performed:

(a) Urine.

For determination of phenolic compounds and organic acids in urine samples, a basal sample (T=0) was taken in a collection bottle. Once the hibiscus-based drink or placebo was ingested, samples were collected at the following times: 3h, 6h, 12h and 24h.

b) Blood

For the studies of inflammation levels (IL-6 and TNF- α), and for the bioavailability of phenolic compounds and organic acids, blood samples were taken with the help of collecting tubes by venous puncture. Eight samples were taken, the first on arrival of the patients at basal time (T=B), then at 30 min (T=2), 1h (T=3), 1:30h (T=4), 2h (T=5), 3h (T=6), 4h (T=7) and 6h (T=8) after having ingested the hibiscus-based drink or the placebo.

In both interventions, patients received a Western diet (breakfast and lunch) characterized by excessive consumption of red meat, simple carbohydrates, ultra-processed products, dyes, saturated fats, refined sugars and very little intake of fiber and vitamins, adjusted to their physical characteristics, and supervised by a team of specialist nutritionists. The participants remained at the trial site without any type of physical exercise during the course of the study and in a relaxed environment with selected recreational activities; they also had a water fountain within their reach from which they could drink indefinitely and a team of medical services that was located at the trial site until its completion.

Sample handling.

For biochemical tests, plasma samples were separated by centrifugation at 3000 rpm for 10 minutes at 4 °C and divided into aliquots and stored at -20 °C until further analysis. On the other hand, urine samples were divided into aliquots and frozen at -20 °C until further analysis.

Extraction of phenolic metabolites and organic acids from biological samples.

A liquid-liquid extraction and protein precipitation with acetonitrile and methanol was used to isolate metabolites from plasma following the procedure described by (Day et al., 2001; Gomez-Juaristi et al., 2018). with some modifications. A thawed plasma sample of 400 μ l was acidified with 10 μ l of 50% (v/v) aqueous formic acid. After shaking the aqueous mixture, it was added dropwise to 900 μ l of cold acetonitrile containing 10% (w/v) ascorbic acid and shaken three times for 20 s before centrifugation at 14000 rpm for 10 min at 4 °C. The supernatant was decanted and the pellet was again extracted with 900 μ l of methanol. After centrifugation (14000 rpm, 10 min 4 °C), the two supernatants were combined and dried under a stream of nitrogen at 30 °C. The dried samples were resuspended in 150 μ l of aqueous formic acid (0.1% v/v) containing 10% acetonitrile acidified with 0.1% formic acid and centrifuged at 4°C for 15 min at 14000 rpm. The final supernatant was collected, filtered (0.45 μ m pore size, cellulose acetate membrane filters, millipore) and 30 μ L was analyzed by HPLC-DAD-MS. Urine samples were diluted with an equivalent volume of HPLC-grade water and centrifuged at 14000 rpm (10 min, 4 °C). The supernatants were filtered (cellulose acetate membrane filters with a pore size of 0.45 μ m, millipore) and a 5 μ L aliquot was directly injected into the HPLC-DAD-MS apparatus.

Characterization and quantification of phenolic compounds and organic acids from H. sabdariffa hibiscus-based beverage and biological samples by HPLC-DAD-MS.

The phenolic fraction and organic acids of the H. sabdariffa hibiscus-based beverage and the placebo beverage provided by Nutriyé were characterized. Where an aliquot of each beverage was filtered through a 0.45 μ m millipore pore size filter and separately injected under gradient conditions into an HPLC high-performance liquid chromatograph coupled to an Agilent 1260 series mass spectrometer (Agilent Technologies, Santa Clara, CA, USA) equipped with a UV-Vis diode array detector (DAD).

Metabolite identification in plasma and urine samples was carried out in the same system performed by the following methodology according to Mateos et al., (2016), using 30 μl of plasma and 5 μl of urine were injected separately under isocratic conditions in a high-performance liquid chromatograph (HPLC-DAD-MS) coupled to a mass spectrometer (Agilent 1260). Water (Phase A) and acetonitrile (Phase B) acidified with 0.1% formic acid at a flow rate of 0.4 ml/min were used as mobile phase. The phase was initially programmed with 95% of solvent A and then 5% of B. The elution program was increased to 10% of solvent B in 10 min and 60% of solvent B in 5 min, which was maintained for 2 min. The initial conditions (5% of solvent B) were recovered 1 min and maintained for 2 min. The conditions for the mass chromatograph were as follows. Identification of CF and organic acids was carried out using an Agilent 1260 series HPLC system (Agilent Technologies, Santa Clara, CA, USA) equipped with a UV-Vis diode array detector (DAD). Samples were injected onto a Poroshell 120 EC-C18 column (4.6 mm \times 150 mm, particle size 2.7 μm) (Agilent Technologies). Detection will be performed in a specific nm range. For MS analysis, an Agilent Quadrupole LC / MS 6120 equipped with an electrospray ionization interface in negative ionization mode will be used with specific conditions of: drying gas flow; nebulizer pressure; gas drying temperature; and capillary voltage. Data analysis was performed using OpenLab CDS ChemStation Edition software (Agilent Technologies, Santa Clara, CA, USA). Characterization was based on retention time and mass spectrometry data. Compounds were first detected using a single MS scan in the specific range (m/z), followed by a targeted search based on peaks showing major signals in the UV-Vis chromatograms. Due to the lack of standards for phase II metabolites, tentative quantification of calibration curves corresponding to phenolic compounds and precursor organic acids was performed. The urine results will be normalized with the volume excreted in each interval studied.

Enzyme inhibition.

In vitro gastrointestinal digestion of the beverages.

Samples will be subjected to an in vitro digestion model adapted from the methodology by Blancas-Benitez et al., (2018). First, the samples will be subjected to an enzymatic hydrolysis process with pepsin at a temperature of 37°C for 1 h (step 1); the phenolic compounds (FC) released in the supernatant at this stage are considered as the FC present in the gastric fraction (GasF). Subsequently, the samples are hydrolyzed with pancreatin 5 mg/ml, P-1750, Sigma Aldrich) and α -amylase (120 mg/ml, A-6255, Sigma Aldrich) (step 2). The CF released at this stage of digestion is considered the CF present in the intestinal fraction (IntF).

α -amylase activity.

The products obtained from the various stages of sample digestion will be used to determine the α -amylase enzyme activity (U/mL) using the kinetic method proposed in the specifications of the amylase activity assay kit (Sigma-Aldrich #MAK009), which consists of taking an aliquot of 50 μ L of the various samples and depositing them in a 96-well plate, then mixed with 100 μ L of master solution, previously prepared with 50 μ L of amylase assay buffer and 50 μ L of α -amylase substrate mixture, then incubated at 25°C and at minute 3, the absorbance at 405 nm is measured to obtain the initial time (T-initial) using the Synergy HT microplate reader (Biotek Instruments, Inc. , USA), readings will be taken every 5 min until the values of the samples approach that obtained at the highest concentration of the standard (20 nM/well) giving rise to the T-final. A calibration curve will be performed with Nitrophenol at concentrations of 4, 8, 12, 16 and 20 nM/well. One enzyme unit is the amount of amylase that cleaves ethylidene-pNP-G7 to generate 1 mM p-Nitrophenol per min. The enzyme activity will be expressed as percentage inhibition (I%) and determined with the equation (Eq 6.1):

$$I\% = \frac{(B \times \text{Factor de dilución})}{\text{Tiempo de reacción} \times V} \quad \text{Ec 4.1}$$

Where:

B refers to the amount of Nitrophenol generated, reaction time is the T-final minus T-initial in minutes and V denotes the volume of sample added to the well (μ L).

α -glucosidase activity.

The inhibition of α -glucosidase of the beverages will be evaluated using the products of the different phases of the in vitro digestion and will follow the methodology described in the specifications of the α -glucosidase kit (Sigma-Aldrich #MAK123) where first 220 μ L of deionized water will be placed in a well of a reading plate and in another well 20 μ L of deionized water will be placed and 200 μ L of calibrator will be added to one of them. From the samples previously prepared in 50 mM phosphate buffer (pH 7.0) 20 μ L will be taken and placed in separate wells and 200 μ L of master solution will be transferred to each of them, the solution will be previously prepared with 200 μ L of p-nitrophenyl- α -D-glucopyranoside (NPG) buffer and 8 μ L of NPG substrate, then incubated at 37° C and absorbance will be measured at 405 nm using Synergy HT microplate reader

(Biotek Instruments, Inc., USA), the initial measurement (T-initial) will be read and after 20 minutes the final absorbance (T-final) will be taken.

The enzyme activity will be expressed in units per liter (unt/L) and calculated with the equation (Eq 6.2) where one enzyme unit is the amount of α -glucosidase that catalyzes the hydrolysis of 1 mM p -nitrophenyl- α -D-glucopyranoside per minute at pH 7.0.

$$\text{unt/L} = \frac{(\text{Abs final} - \text{Abs inicial})}{\text{Abs del calibrador} - \text{Abs del agua}} \times 250 \text{ unt/L} \quad \text{Ec 4.2}$$

Where:

Abs of the calibrator is the value for the calibrator at 20 minutes, Abs of the water represents the value of the water at 20 minutes and unt are units.

Evaluation of glycemic response.

To obtain the biological sample, a lancet will be used to puncture the thumb of the volunteer's finger and the sample will be collected on highly sensitive test strips for capillary glucose measurement of the OneTouch Ultra® System.

The portable system used for pre- and postprandial glucose measurement allows the monitoring of capillary glycemic response under experimental conditions for healthy subjects. With the use of this equipment, measurements will be obtained from t_0 (preprandial), and at 15, 30, 45, 60, 90 and 120 min (postprandial). The results will be expressed in mg/dL.

Insulin analysis.

Participants will be required to hold a hand warmer ($\sim 40^\circ\text{C}$) for 5 min before each capillary blood sampling, to stimulate peripheral blood flow.

Blood samples (approx. 250 μL , 4-5 drops) will be drawn through finger pricks (OneTouch Ultra® lancets). Measurements over time will be similar to the glycemic response assessment technique. Samples will be placed in BD Microtainer SST tubes and kept at room temperature for 30 min. Samples will then be centrifuged

(5000 rpm, 25°C) for 10 min to obtain serum and kept in a freezer at -20 degrees Celsius until further analysis (Hossain et al., 2021).

Serum insulin concentrations will be analyzed using a two-site solid-phase enzyme immunoassay kit (Human Insulin ELISA Kit, Millipore, EZHI-14K), where the direct sandwich technique is used with two antibody solutions targeting insulin epitopes (Figure 6. 2) in such a way that the plate will be coated with a monoclonal antibody (capture) and then the sample will be added, so that the analyte of interest (insulin) will bind with the capture antibody and subsequently a horseradish peroxidase-labeled detection secondary antibody will be added, this antibody will bind to the antigens that will be in turn bound to the capture antibody, consequently will be added the substrate 3,3',5,5'- tetramethylbenzidine in buffer (TMB), forming a bluish coloration dependent on the insulin concentration, the reaction will be terminated by the addition of stop solution (HCl) obtaining as colored product (yellow) after acidification, which is quantifiable at 450 nm in a microplate reader (BioTek®, Synergy HT, Winooski, Vermont, USA). The results will be expressed in $\mu\text{U/L}$.

Statistical Analysis.

Statistical analysis: first stage

The normality of the data distribution will be evaluated by means of the Shapiro-Wilk test; if so, a Student's t-test will be used, or, on the contrary, a nonparametric Mann-Whitney test will be used to evaluate the statistical differences between the variables. The level of statistical significance will be a value of ($p < 0.05$). Statistical analysis will be performed with the STATISTICA program, version 10 (Statsoft.1984-2011 Inc., Tulsa, OK, USA).

Statistical analysis: second stage

Each sample will be considered as an experimental unit. Statistical analysis will be performed with the STATISTICA program, version 10 (Statsoft. 1984-2011 Inc., Tulsa, OK, USA). Differences in the response variables in the samples will be evaluated through a repeated-means ANOVA analysis. The level of statistical significance will be a value of ($p < 0.05$).

Calculation of the area under the curve.

The glycemic and insulinemic values obtained experimentally will be recorded in a database. The area under the curve (AUC) will be calculated according to the equation proposed by Wolover and Jenkins (1986) (Eq.4.7.):

$$AUC = \left(\left(A + B + \frac{D}{2} \right) * 15 \right) + \left(\left(\frac{D}{2} + \frac{E}{2} \right) * 30 \right) + \left(\left(\frac{E^2 * 30}{2} \right) * (E + F) \right) \quad \text{Ec 4.7.}$$

Where A, B, C, D, E, F; represent the increase in glucose and insulin above baseline and 15 and 30 represent the time interval between blood samples. Any area below the fasting level will be discarded.

TECNOLÓGICO
NACIONAL DE MÉXICO

EXPECTED RESULTS

ITESO, Universidad
Jesuita de Guadalajara

This research aims to identify which metabolites are bioavailable in plasma and urine samples after ingestion of a hibiscus drink and to identify inflammation markers in the same normal-weight volunteers, as a potential adjuvant in the management of inflammation caused by COVID-19 disease, and generate a hypoglycemic effect by reducing the levels of glucose and serum insulin, consequent to the generation of possible modifications on the physiological mechanisms, including the inhibition of the activity of the α -amylase and α -glucosidase enzymes by the action of the bioactive compounds, as well as by the interaction with the rest of the ingredients that compose the beverage of interest.

- Abdel-Rahman, R. F., Hessin, A. F., Abdelbaset, M., Ogaly, H. A., Abd-Elsalam, R. M., & Hassan, S. M. (2017). Antihypertensive Effects of Roselle-Olive Combination in L-NAME-Induced Hypertensive Rats. *Oxidative Medicine and Cellular Longevity*, 2017. <https://doi.org/10.1155/2017/9460653>
- Abubakar, S. M., Ukeyima, M. T., Spencer, J. P. E., & Lovegrove, J. A. (2019). Acute effects of hibiscus sabdariffa calyces on postprandial blood pressure, vascular function, blood lipids, biomarkers of insulin resistance and inflammation in humans. *Nutrients*, 11(2). <https://doi.org/10.3390/nu11020341>

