In vitro models provide a first and valuable insight into the transformations of bioactive compounds (BCs) during their gastric processing before reaching the target tissues. Human and animal models have been used to study the bioavailability and metabolism of BCs by *in vivo* assays. Each model has its advantages and disadvantages, some are the established ethical aspects, the Declaration of Helsinki (Osuna et al., 2016) must be taken into account, in addition to the possible ethical requirements of each institution and country. For human models, the informed consent of the volunteers is required (Fernández-Ochoa et al., 2022). The first step metabolism consists of the bioactive compound crossing the intestinal barrier before reaching the systemic circulation, at this point it is crucial to take into account whether it is an oral intake, whether the CB is free from the food matrix, encapsulated or in emulsion because it has to be able to cross the epithelial barrier. The second step is bioavailability, many researches focus on assessing the bioavailability of CBs, this means the proportion of an administered CB that is able to reach the systemic circulation and is a function of the opposite processes of absorption and clearance and can be calculated by considering the area under the curve (ABC) of the initial concentration of the CB between the amount found in the ABC at the intravenous level. The bioavailability of CBs, mainly phenolic CF compounds, is highly variable and it has been reported, for example, that flavonoids are very poorly absorbed glycosides that require the presence of β -glucosidases enzymes found in the small intestine before being absorbed as aglycones (Ávila-Román et al., 2021).

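### Bioavailability is the first-named objective, but the plan derives no exposure measure for any metabolite, and its urine normalisation leaves time profiles open to distortion

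*Combined protocol and SAP*

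**What the plan says.** All references are to the combined protocol and SAP.

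- **Objectives.** The general objective opens with in vivo bioavailability. Specific objective 3 begins "To evaluate the bioavailability of organic acids and phenolic compounds in urine and plasma samples". Specific objective 4 then relies on whichever metabolites are found to be bioavailable.
- **Background on bioavailability in clinical trials.** Bioavailability is described as "the proportion of an administered CB that is able to reach the systemic circulation", which "can be calculated by considering the area under the curve (ABC) of the initial concentration of the CB" relative to an intravenous area. The trial has no intravenous administration.
- **Acute Trial Clinical Intervention.** Each participant takes one product and, after a washout of more than 6 days, the other. For urine, after a basal sample, "samples were collected at the following times: 3h, 6h, 12h and 24h". For blood, "Eight samples were taken, the first on arrival of the patients at basal time (T=B"), then 0.5, 1, 1.5, 2, 3, 4 and 6 h after the drink.
- **Characterization and quantification by HPLC-DAD-MS.** "The urine results will be normalized with the volume excreted in each interval studied". No formula or unit follows. Phase II metabolites are quantified tentatively against precursor compounds.
- **Statistical Analysis.** The first stage applies Shapiro-Wilk and then Student's t-test; otherwise "a nonparametric Mann-Whitney test will be used to evaluate the statistical differences between the variables". The second stage is a repeated-measures ANOVA on response variables that are not named.
- **Calculation of the area under the curve.** "The glycemic and insulinemic values obtained experimentally will be recorded in a database", and the AUC equation is applied to those values. Metabolites are not mentioned.

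**The concern.** An objective about bioavailability needs a quantity that expresses how much of a compound appeared in plasma or urine. The plan stops at concentrations. Without a defined measure, the answer to the lead objective could be assembled in several ways once the data are seen: peak value, value at a chosen time, number of times above baseline, or simple detection. Specific objective 4 inherits the problem, because nothing says when a metabolite counts as bioavailable.

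Two further points bear on how any result would be read. Mann-Whitney is a test for independent groups, whereas here the same people take both drinks, so it would discard the pairing that the crossover provides. The plan does not say whether its t-test is paired. The urine sentence can also be read in more than one way, and at least one natural reading makes late intervals look larger only because they are longer.

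**Working it through.** **Step 1. Is there a planned figure to reproduce?** No. The documents give no exposure quantity, formula or target for any metabolite, so the check is an inventory followed by direct arithmetic.

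**Step 2. Inventory of exposure measures**

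| Measure | Glucose, insulin | Metabolites |
|---|---|---|
| AUC | planned | not planned |
| Cmax, Tmax | not defined | not defined |
| Urinary rate per interval | not applicable | not defined |
| Cumulative urinary amount | not applicable | not defined |
| Percent of dose recovered | not applicable | not defined |

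**Step 3. Could the samples support such measures?** Plasma times are 0, 0.5, 1, 1.5, 2, 3, 4 and 6 h. The gaps are 0.5 + 0.5 + 0.5 + 0.5 + 1 + 1 + 2 = 6 h, so a trapezoidal AUC0-6h, Cmax and Tmax can be computed. The normalisation sentence presupposes that urine volume is measured in each interval, so amounts and rates can be computed too.

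**Step 4. Urine intervals.** The lengths are L = 3 - 0, 6 - 3, 12 - 6 and 24 - 12, that is 3, 3, 6 and 12 h. Assume constant excretion r = 1 unit/h and constant urine flow f. Then amount A = rL, volume V = fL and concentration C = A/V = r/f. Scaled to the first interval:

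| Reading of the normalisation | 0-3 h | 3-6 h | 6-12 h | 12-24 h |
|---|---|---|---|---|
| Concentration x volume (A = 3, 3, 6, 12) | 1 | 1 | 2 | 4 |
| Plain concentration (r/f) | 1 | 1 | 1 | 1 |
| Concentration / volume (r/(f²L)) | 1 | 1 | 0.5 | 0.25 |
| Amount per hour (A/L) | 1 | 1 | 1 | 1 |

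These ratios do not depend on the value of f. The first reading is the most natural one. Its rise starts after 6 h and reaches 12/3 = 4. Plain concentration is flat only while flow is constant, and participants at the site had free access to water.

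**Step 5. Sensitivity to the excretion profile.** Constant excretion after a single drink is only an illustration. Assume instead a mono-exponential decline with half-life h, so that k = ln 2 / h and the amount between times a and b is proportional to exp(-ka) - exp(-kb). The half-lives are assumptions; the documents give none.

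| Assumed half-life | Amount per interval | Amount per hour |
|---|---|---|
| 4 h | 1 : 0.60 : 0.56 : 0.27 | 1 : 0.60 : 0.28 : 0.07 |
| 12 h | 1 : 0.84 : 1.30 : 1.57 | 1 : 0.84 : 0.65 : 0.39 |
| 24 h | 1 : 0.92 : 1.61 : 2.50 | 1 : 0.92 : 0.81 : 0.62 |

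At 12 h a falling rate appears as a late rise in amount. At 4 h amounts fall in every interval, as they do at 2 h (1 : 0.35 : 0.17 : 0.02).

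**Step 6. Effect on hibiscus versus placebo.** Assume hibiscus excretion is 1.5 times placebo throughout. The interval amounts are 4.5/3, 4.5/3, 9/6 and 18/12, a ratio of 1.5 each time. Interval length cancels.

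**Step 7. Basal urine.** No collection interval is stated for it, so it cannot be placed on an amount or rate scale with the later samples.

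**The case against.** The strongest reply is that the trial does not promise an extent of absorption. The Expected Results section speaks of identifying which metabolites are bioavailable, and the background accepts measuring metabolites in plasma and urine as a way to evaluate bioavailability. On that view, detection is enough. This has some force, but it does not close the gap: no criterion for calling a metabolite bioavailable is given, and serial sampling to 6 and 24 h with volume-normalised urine goes well beyond detection.

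Several stronger readings are tempting and are not supported:

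- A reader might infer that the plan sets absolute bioavailability against an intravenous reference as its own standard and then fails it. That description is in the literature review, not in the methods.
- A reader might infer that the urine results will show a fourfold rise. This needs both the amount-per-interval reading and constant excretion. The text fixes neither, and the background itself says phenols rise only transiently in plasma after a single dose.
- A reader might infer that ANOVA, or a separate test at every sampling time, is planned for urine. The statistical section assigns no method to urine or plasma metabolites and does not mention tests by time point.
- A reader might infer that the drink comparison is biased by interval length. Within the same interval it is not.

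It is also fair to say that a full repair may be out of reach. Sampling is described in the past tense, so the time of the last void before the basal sample may not be recoverable. The 60 ml volume is clearly attached only to the placebo, and completeness of urine collection is not described.

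**Conclusion.** The main point holds without any numerical assumption: the first-named objective has no exposure measure for any metabolite, although the sampling supports one. Followed as written, the trial can report lists and concentration comparisons but no extent of exposure, and the nonparametric branch would ignore the within-person design.

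The urine point is conditional. If results are expressed as amount per interval, unequal lengths distort time profiles from 6 h onward. The size is 1 : 1 : 2 : 4 under constant excretion, smaller under a slow decline, and not enough to produce a rise at assumed half-lives of 4 h or less. It does not touch hibiscus versus placebo within an interval. This deserves a change before analysis because better measures are available at little cost; it is not evidence that the drink comparison is invalid.

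**What to change.** Before analysis, state for each compound, with units:

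- **Plasma:** baseline-corrected AUC0-6h, Cmax and Tmax.
- **Urine:** amount = concentration x volume, reported as amount per hour in each interval, and the cumulative amount over 0-24 h (Ae0-24h). Keep the basal sample off the rate scale unless its collection interval is known.
- **Comparison:** hibiscus against placebo within person, by a paired or crossover analysis, on AUC0-6h and Ae0-24h. This replaces Mann-Whitney for these outcomes.
- **Percent of dose:** report it only if the volume of hibiscus drink is confirmed and urine collection was complete. Label it approximate, because conjugates are quantified as precursor equivalents.
- **Wording:** describe the results as relative exposure and urinary recovery, not absolute bioavailability.

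The cost is modest extra analysis on samples already described. The limits are that recovery remains approximate and that plasma exposure after 6 h is not captured.

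### The plan does not say how drink order was assigned and names no period term, so a visit effect could bias the drink contrast (uneven orders) or cost power (balanced orders)

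*Combined protocol and SAP*

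**What the plan says.** The design is under General methodology, Acute Trial Clinical Intervention: "An acute single-blind trial was conducted". At the first visit, "Participants consumed a hibiscus-based drink (*H. sabdariffa*), or a 60ml placebo drink". The two visits are more than six days apart. Of the later visit the protocol says that "the participants underwent a second intervention with a different product from the first one (beverage to be evaluated or placebo, as appropriate"). The Participants section gives the size: "Twelve normo-weight volunteer participants without any medical condition were included".

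No part of the design or methods mentions randomisation, counterbalancing, sequence groups, an allocation ratio or concealment. The word randomized occurs only in titles in the reference list.

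Under Statistical Analysis, first stage, a Shapiro-Wilk check decides the test: "a Student's t-test will be used, or, on the contrary, a nonparametric Mann-Whitney test will be used". Whether the t-test is paired is not stated. For the second stage, "Differences in the response variables in the samples will be evaluated through a repeated-means ANOVA analysis". Its factors are not listed. Neither stage mentions period or sequence.

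Under Calculation of the area under the curve, glucose and insulin areas are built from increases above baseline.

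**The concern.** In a two-period crossover each person supplies one drink difference, and that difference contains any change between the visits. The change enters with one sign for people who had hibiscus second and the opposite sign for those who had it first. It cancels from the mean difference only if the two orders are equally frequent, and even then it adds spread unless period is modelled.

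Visit differences are plausible here. The gap between visits has a minimum but no maximum. Infection or inflammatory disease is screened for the six weeks before the study, but no re-check before the second visit is described, and IL-6 and TNF-α are outcomes. Samples are frozen for later assay, with no rule that one person's two visits are assayed together. Familiarity with repeated punctures may also change the response.

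If the orders were uneven, part of such a change would be read as an effect of hibiscus. If they were balanced, a real effect could be missed.

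**Working it through.** The documents give no SD, target effect, power or sample-size derivation, so there is no stated figure to reproduce. What follows illustrates size.

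**Inputs.** From the documents: n = 12, two visits, significance level 0.05. Assumed: a two-sided paired t-test; a visit shift π of 0.5 or 1.0, in SDs of the within-person difference; for power, a true drink effect of 0.9 SD.

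**Bias.** With a people taking hibiscus second and b taking it first (a + b = 12), the expected drink contrast when there is no drink effect is π × (a − b)/12. At 9:3 this is 6/12 = one half of π. At 8:4 it is 4/12 = one third. At 6:6 it is 0.

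**False-positive rate.** Rates are simulated with 100,000 runs, except 12:0, which uses the noncentral t with 11 df and noncentrality π√12 (for π = 0.5, 1.73).

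| Split | Share of shift left as bias | No period term, π = 0.5 | No period term, π = 1.0 | With period term |
|---|---|---|---|---|
| 6:6 | 0 | 2.9% | 0.7% | about 5% |
| 8:4 | 1/3 | 5.6% | 5.2% | about 5% |
| 9:3 | 1/2 | 9% | 15% | about 5% |
| 10:2 | 2/3 | 15% | 36% | about 5% |
| 12:0 | all | 35% | 88% | cannot be fitted |

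At 8:4 the error rate hardly moves because the shift also widens the spread of the differences. The estimate is still biased.

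**Power at 6:6, true effect 0.9 SD.** Without a period term the expected variance of the differences rises from 1 to 1 + π² × 12/11:
- π = 0.5: variance 1.27, SD 1.13, simulated power 73%.
- π = 1.0: variance 2.09, SD 1.45, simulated power 50%.

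With the period term (10 df), power is 80.2% whatever the shift. With no shift and no period term (11 df) it is 81.0%. The term therefore costs 0.8 percentage points at 6:6.

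**Cost of the term at uneven splits.** The adjusted contrast has standard error ½√(1/a + 1/b) in SD units: 0.289 at 6:6, 0.306 at 8:4 and 0.333 at 9:3. For a 0.9 SD effect the noncentralities are 3.12, 2.94 and 2.70, and with 10 df the power is 80%, 75% and 68%. Balance is therefore worth having as well as the term.

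**How often chance gives imbalance.** Simple randomisation of 12 gives 9:3 or worse with probability 2 × (220 + 66 + 12 + 1)/4096 = 14.6%. This is the reason to fix the split at 6:6.

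**The case against.** Several points on the other side have force.

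- **A single fixed order is not what the text suggests.** A reader might infer that all 12 had the same order and quote the 35% figure. The protocol offers hibiscus and placebo as alternatives at each visit, which points to both orders being used. The 12:0 row is a worst case only.
- **Nothing says that staff chose the order.** The qualifier closing the bracket in the crossover sentence might be read that way. Its natural meaning is whichever product the person had not yet taken. The documents are silent on assignment, so order may have been randomised and not reported. A scheme announced at that point is not shown. It is introduced as a sampling scheme but might also have displayed the order.
- **A period term is not ruled out.** The second-stage ANOVA lists no factors, so the accurate statement is that period is not named.
- **The plan does not specify a paired test.** Mann-Whitney is an unpaired test, and pairing of the t-test is not stated. With an unpaired t-test and an assumed within-person correlation of 0.5, the 9:3 rates are 3% (π = 0.5) and 10% (π = 1.0). That test is conservative to begin with (0.9% with no shift), and the bias in the mean difference is the same.
- **Baselines help.** Each visit has its own baseline, and the glucose and insulin areas use increases above it, so a constant visit offset largely cancels. A change in the size of the response does not cancel, and no baseline correction is stated for IL-6 or TNF-α.

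These points limit the size of the concern. They do not supply an order rule, a split or a period term.

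**Conclusion.** The concern holds in a limited form. Order assignment and the split are not stated, and no period term is named. Under the paired-test illustration the consequence depends on the split:

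- At 9:3 there is bias of half the visit shift and a false-positive rate of 9% to 15%.
- At 8:4 there is bias of one third of the shift with almost no change in the error rate.
- At 6:6 there is no bias, but power falls from 80% to between 73% and 50%.

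These figures rest on assumed visit shifts of 0.5 to 1.0 SD, a paired two-sided test and, for power, a 0.9 SD effect. None of these comes from the documents. IL-6 and TNF-α are more exposed than the baseline-corrected glucose and insulin areas. The documents do not support a conclusion that drink and visit are fully confounded.

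**What to change.** For any visits not yet done, allocate order at random from a concealed list, six participants hibiscus-first and six placebo-first, and say so in the design section.

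Analyse the in vivo outcomes (plasma and urine metabolites, IL-6, TNF-α, glucose, insulin) with drink and period as fixed effects and participant as the block. For a single summary per visit this is the same as comparing visit 2 minus visit 1 differences between the two sequences. It does not apply to the in vitro enzyme assays, which have no participants or visits.

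Much of the design text is in the past tense, so the visits may be complete. In that case report how order was assigned and how many participants had each order, and fit the period term if both orders were used. If only one order was used, the term cannot be fitted. State as a limitation that drink and visit cannot be separated.

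The cost is one sentence in the design and one degree of freedom, with no added participants or samples. When there is no visit effect, that is under one percentage point of power at 6:6. It is more at an uneven split: for a 0.9 SD effect, power with the term is 75% at 8:4 and 68% at 9:3.
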